#### 5.3 Secondary outcome analysis

Bone density measures will be analysed in an intention to treat approach, using a linear mixed model. Data from all available time points will be used. Normal distribution will be checked and data transformations will be performed if necessary if assumptions of normality are not reached. P-values and estimated marginal means will be calculated at different time points.

In addition, percentage changes in BMD and the percentage of patients with a BMD loss higher than the least significant change (LSC), which represents the smallest difference between successive measurements of BMD that can be considered a real change, will calculated. Here no intention to treat approach will be used.

The number of patients exceeding reference ranges will be calculated with an intention to treat approach, where drop-outs will be considered as non-responders. A Fisher's exact test was used to assess differences in patient numbers exceeding reference ranges between both treatment groups.

All statistical tests were two-tailed and a p-value below 0.05 ( $\alpha$ ) was considered statistically significant.

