3.1 Study design and schematic

This is a randomized study to investigate the effect of effervescent alendronate on BTM after denosumab discontinuation.

At the earliest three months but no later than four months after the last denosumab injection, 40 subjects will be randomized to effervescent alendronate administered for either 24 (n=20) or 48 weeks (n=20). The randomization code will be generated by a randomization manager. Randomization will be done in blocks of four.

Study schematic

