4.1. Composition and dosing

After denosumab discontinuation subjects will be randomized to receive open label effervescent alendronate (Steovess) for 24 or 48 weeks. Effervescent alendronate a bisphosphonate as effervescent tablets that should be taken once a week. Each effervescent tablet contains 70 mg alendronic acid as 91.37 mg of alendronate sodium trihydrate. Excipients are sodium dihydrogen citrate, citric acid anhydrous, sodium hydrogen carbonate, sodium carbonate anhydrous, strawberry flavour [Maltodextrin (Maize), arabic gum, propylene glycol (E 1520), nature-identical flavouringsubstances], acesulfame potassium and sucralose. Each tablet contains 602.54 mg of sodium. Effervescent alendronate is supplied as a white to off-white round effervescent tablets of 25 mm diameter, flat faced with bevelled edges.

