4.5. Administration way

Effervescent alendronate 70 mg should only be taken upon arising for the day dissolved in half a glass of plain water (not less than 120 ml or 4.2 fl.oz.). Dissolving the tablet in water yields a buffered solution of pH 4.8 - 5.4. The buffered solution should be drunk, once the fizzing has subsided and the effervescent tablet has completely dissolved to give a clear, colourless, buffered solution, followed by at least 30 ml (one sixth of a glass) of plain water. Additional plain water may be taken. Patients should not swallow the undissolved effervescent tablet, should not chew the effervescent tablet or allow the effervescent tablet to dissolve in their mouths because of the risk for oropharyngeal irritation. Patients should not lie down for at least 30 minutes after taking effervescent alendronate 70 mg.

Steovess will be distributed during study visits. Subjects should take one 70 mg effervescent tablet once weekly at home. Patients should be instructed that if they miss a dose of alendronate 70 mg, they should take one effervescent tablet on the morning after they remember. They should not take two effervescent tablets on the same day but should return to taking one effervescent tablet once a week, as originally scheduled on their chosen day.

August 09 2019 – Version 1.0

Alendronate 70 mg must be taken at least 30 minutes before the first food, beverage, or medicinal product of the day with plain water only. Other beverages (including mineral water), food and some medicinal products are likely to reduce the absorption of alendronate.

Patients are requested not to take any study medication on the morning of a planned visit (week 12, week 24 or week 48): this accounts for the study medication (Steovess) and the calcium/ vitamine D supplements.

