## 4. Outcome measures

#### 4.1 Primary endpoints

The primary end point of this study is to investigate if effervescent alendronate is able to maintain bone turnover markers after discontinuation of denosumab in a non-osteoporotic population. The outcome measures being used for this are the bone turnover markers CTX-I (C-terminal telopeptide of type I collagen) a marker that reflects the breakdown of bone and PINP (N-terminal propeptide of type I collagen) a marker that reflects the formation of new bone. The primary end point will be the difference in these bone turnover markers after 48 weeks between both treatment arms.

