#### 4.2 Secondary endpoints

Secondary end points are changes in bone mineral density (BMD) at the femoral neck and spine at week 48, the number of patients from both groups maintaining CTX-I and PINP levels within reference range values at week 12, 24 and 48. Reference ranges used will be adjusted according to menopausal status and sex. Percentage changes in BMD and the percentage of patients with a BMD loss higher than the least significant change (LSC), which represents the smallest difference between successive measurements of BMD that can be considered a real change, will be calculated.

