### 5.2 Primary outcome analysis

The primary outcome analysis will be performed in an intention to treat approach, where drop-outs were considered as non-responders. Changes in bone turnover marker levels will be analysed with a linear mixed model. Data from all available time points will be used. Normal distribution will be checked and data transformations will be performed if necessary if assumptions of normality aren't reached. P-values and estimated marginal means will be calculated at different time points.

All analyses will be performed with a two-sided p-value. A p-value below 0.05 (p<0.05) will be considered statistically significant.

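### Planned treatment is the same in both arms until week 24, so SAP 5.2 and 5.3 should limit between-arm tests to week 48 and state how baseline enters that contrast

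*SAP*

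**What the plan says.** Protocol 3.1 randomises 40 subjects, 20 per arm, to 24 or 48 weeks of one product. Protocol 4.1 describes it as "open label effervescent alendronate (Steovess) for 24 or 48 weeks", and Protocol 4.5 gives both arms the same instruction: "Subjects should take one 70 mg effervescent tablet once weekly at home". Protocol 4.5 also asks patients to take no study drug on the morning of the week-12, week-24 or week-48 visit.

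SAP 4.1 fixes the primary contrast: "The primary end point will be the difference in these bone turnover markers after 48 weeks between both treatment arms". SAP 5.2 describes the model in one sentence, "Changes in bone turnover marker levels will be analysed with a linear mixed model", and adds that "P-values and estimated marginal means will be calculated at different time points". It lists no fixed effects, baseline term or covariance. SAP 5.1 compares only demographic baseline data between arms.

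SAP 4.2 lists as a secondary endpoint "the number of patients from both groups maintaining CTX-I and PINP levels within reference range values at week 12, 24 and 48". SAP 5.3 states that a Fisher's "exact test was used to assess differences in patient numbers exceeding reference ranges between both treatment groups". That sentence names no visit. SAP 5.3 repeats the time-point wording of SAP 5.2 for BMD. The significance threshold throughout is a two-sided 0.05.

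**The concern.** The trial asks two questions: whether alendronate keeps bone turnover in range after denosumab, and whether 24 and 48 weeks of it differ. Up to week 24 only the first can be answered, because the arms have not yet diverged. A between-arm p-value at week 12 or 24 has no duration effect to detect. A small one would reflect chance, behaviour under open-label allocation, visit timing or differential drop-out, yet it could be reported as a duration effect. Nothing in the SAP marks early by-arm comparisons as descriptive, and no pooled estimate at those visits is stated.

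The week-48 contrast is the informative one. It rests on 20 per arm with no sample size calculation (Protocol 11.3). The wording of SAP 5.2 fits at least three analyses: an unadjusted change score, free arm means at each visit, or a model that uses baseline as a response or covariate. They can differ in precision, and the choice is left open.

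**Working it through.** The plan states no power, SD, correlation or in-range rate, so it has no figure to reproduce. The inputs from the documents are 20 per arm, two markers, visits at weeks 12, 24 and 48, and a two-sided 0.05. Everything else below is an assumption.

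**1. What early Fisher tests could do.** If the test is applied at every visit listed in SAP 4.2, there are 2 markers × 3 visits = 6 tests. Of these, 2 × 2 = 4 fall where planned treatment is identical. Exact enumeration of the two-sided Fisher test at 20 v 20, with the same true in-range rate in both arms, gives:

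| True in-range rate | 50% | 60% | 70% | 80% | 90% | 95% |
|---|---|---|---|---|---|---|
| Actual size | 2.04% | 2.38% | 2.48% | 2.26% | 1.18% | 0.19% |

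The chance of any false positive over the four is therefore no more than about 4 × 2.5% = 10%. At an in-range rate of 90% it is no more than 4 × 1.18% = 4.7%.

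**2. If the SAP 5.2 p-values are also between-arm.** Four independent null tests at 0.05 give 1 − 0.95^4 = 18.5%. Without independence the bound is 4 × 0.05 = 20%. Week-24 BMD tests would add to this.

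**3. What the early visits can estimate.** Pooling to n=40 takes the 95% half-width of a mean from 0.468 SD (n=20) to 0.320 SD. For an illustrative 90% in range, the Clopper-Pearson interval is 68.3% to 98.8% for 18/20 and 76.3% to 97.2% for 36/40.

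**4. Week-48 contrast.** Write r for the correlation between baseline and week 48. Assume unit SD at both visits and complete data.

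- Free arm means: SE = sqrt(2/20) = 0.316.
- Unadjusted change score: SE = sqrt((2/20) × 2(1 − r)). At r = 0.3 this is sqrt(0.14) = 0.374.
- Baseline as covariate, or a common baseline mean: SE = 0.316 × sqrt(1 − r²). At r = 0.3, 0.5 and 0.7 this is 0.302, 0.274 and 0.226.
- Gain of adjustment over free arm means: 1 − sqrt(1 − r²) = 5%, 13% and 29% at those values.
- If correlation decays by a factor of 0.3, 0.5 or 0.7 per 12 weeks, r over 48 weeks is that factor to the fourth power: 0.008, 0.0625 or 0.240. The SE is then 0.316, 0.316 or 0.307, a gain of 0% to 3%.

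With unequal SDs, the unadjusted change score is less precise than the raw week-48 difference when r < SD0/(2 × SD48). That threshold is 0.5 only when the SDs are equal.

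**The case against.** The strongest reply is that the early tests are inferred. SAP 4.2 lists counts at three visits and SAP 5.3 mentions a Fisher test without a visit; neither says outright that arms are tested at weeks 12 and 24. That stands. A reader might infer that such tests are definitely planned, but the text shows only that they are not excluded. The p-values in SAP 5.2 could likewise be within-arm, and its marginal means could be averaged over arms.

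It is also fair that the statistical harm is small. Fisher's test is conservative at this size, the tests are secondary, and SAP 4.1 fixes the primary contrast at week 48. A reader might infer inflated error in the primary result, and nothing in the documents supports that. Nor is pooled information lost if by-arm means are reported with SEs. The arms are independent, so two means each with SE 1/sqrt(20) = 0.224 SD average to sqrt(2 × 0.05)/2 = 0.158 SD, the n=40 value.

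On baseline, a reader might infer that it is ignored. SAP 5.2 uses all available time points, which may include baseline as a response, so the gap is an unstated choice. High correlation cannot be presumed either: baseline falls three to four months after the last denosumab injection, when the protocol expects turnover to rise. The SEs above also assume complete data, whereas SAP 3.2.3 imputes drop-outs as non-responders, in the mixed models as well.

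What remains is that the plan allows uninformative arm tests and leaves open a baseline choice that can matter. SAP 2.3 and Protocol 3.4 give a 48-week treatment duration per subject, which must be reconciled with the 24-week arm; this does not affect sameness before week 24.

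**Conclusion.** The point holds in a limited form. Planned treatment is identical to week 24, so between-arm results at weeks 12 and 24 cannot show a duration effect, and the SAP neither excludes such tests nor labels them descriptive. The risk is chiefly one of interpretation: about 0.2% to 2.5% per early Fisher test, for assumed in-range rates of 95% down to 50%. The 18.5% figure depends on reading the SAP 5.2 p-values as four independent between-arm tests, and is not an upper bound.

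The baseline term is the part that may affect the primary contrast. Its value runs from near nil to 29% of the SE over the correlations considered. The 29% is the r = 0.7 scenario and not a limit. These figures assume equal SDs and complete data, and the documents supply no correlation. Because the baseline value is already collected, the change is worth making even if the gain proves small.

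**What to change.** 1. In SAP 5.2, fit the mixed model with visit and arm-by-visit effects after baseline, with the baseline marker value as covariate or a common baseline mean. State the covariance structure and take the week-48 contrast from this model.
2. In SAP 5.2 and 5.3, make week 48 the only between-arm test for the markers, the reference-range counts and BMD.
3. Report weeks 12 and 24 pooled over all patients with intervals. Keep by-arm values as description and as a check on comparability.

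No new data are needed. The cost is a slightly fuller model specification for a precision gain that may be small. Parts of SAP 5.2 and 5.3 are in the past tense, and SAP 6 schedules analysis from June 2022 to about January 2023. If results already exist, the revised model should be labelled post hoc or a sensitivity analysis, and early by-arm results can still be marked descriptive in the report.

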Main Endpoints	 The primary endpoint of this objective is to assess the number of patients that maintain C-terminal telopeptide of type I collagen (CTx-I) levels within the premenopausal reference range at 48 weeks. Secondary endpoints are the assessment of the number of patients that maintain CTx-I levels within the premenopausal reference range at week 12 and 24 as well as the changes in CTx-I and N-terminal propeptide of type I procollagen (P1NP) levels from baseline until 12, 24 and 48 weeks after randomization to effervescent alendronate. Co-exploratory objectives are changes in T-score at lumbar spine and hip from baseline to week 24 and week 48, and the radiographic changes at the finger joints in terms of new erosive joints and GUSS change between W24 and W48 and baseline. 				
Hypothesis	The main hypothesis is that effervescent alendronate will be able to maintain bone turnover markers within the pre-menopausal reference range, thereby reducing the likelihood of bone turnover associated changes.				
Study Sites	1 site – the UZ Ghent site				
Subjects	40 subjects for the alendronate follow-up study				
Enrolment	72 weeks				
Main Eligibility Criteria	Subject must have completed our three year study 'RANKL-blockade for the treatment of erosive osteoarthritis (OA) of interphalangeal finger joints' (EudraCT number: 2015-003223-53; Protocolnumber: AGO/2015/008)				
Study treatment Duration	48 weeks				

Table of Contents

- Protocol Title and Investigators
- Protocol signature page
- Protocol synopsis

1. Background and Rationale

- 1.1 Disease background
- 1.2 Denosumab
- 1.3 Effervescent alendronate
- 1.4 Rationale for study design
- 1.5 Hypotheses

2. Study Objectives and Endpoints

3. Experimental Plan

- 3.1 Study design and schematic
- 3.2 Number of sites
- 3.3 Number of subjects
- 3.4 Estimated study duration
- 3.5 Subject Eligibility
 - 3.5.1 Inclusion criteria
 - 3.5.2 Exclusion criteria
- 3.6 Criteria for withdrawal

4. Medication

- 4.1 Composition and dosing
- 4.2 Producer
- 4.3 Distributor
- 4.4 Packaging
- 4.5 Administration way
- 4.6 Labelling:
- 4.7 Storage conditions:
- 4.8 Known side effects of the medication
- 4.9 Drug accountability

5. Procedures

- 5.1 Study procedures
- 5.2 Study table
- 5.3 Sample processing

6. Randomisation

7. Reporting requirements for investigational product complaints

- 8. Concomitant therapy
- 9. End of study
- 10. Adverse Events/Adverse Event reporting
 - 10.1. Definitions

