#### 2.3 Study design

This is a monocentric randomized study to investigate the effect of effervescent alendronate on bone turnover markers after denosumab discontinuation. At the earliest three months but no later than

four months after the last denosumab injection, 40 subjects will be randomized to effervescent alendronate administered for either 24 (n=20) or 48 weeks (n=20). The randomization was performed by a randomization manager. The total treatment duration per subject is 48 weeks.

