### 3.2.2 Full analysis dataset

The full analysis set will include all patients who are randomly allocated to a treatment group and received at least 1 dose of effervescent alendronate.

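### Fisher's exact test for the reference-range counts is valid but conservative; Boschloo's exact test would recover some power at no cost in error control, mainly if the arms stay equal

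*SAP*

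**What the plan says.** SAP 5.3 states that a Fisher's "exact test was used to assess differences in patient numbers exceeding reference ranges between both treatment groups". The level is set in the same section: "All statistical tests were two-tailed and a p-value below 0.05" counts as significant. Drop-outs stay in the denominator, "where drop-outs will be considered as non-responders".

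SAP 2.3 plans 40 patients, 20 per arm, and Protocol 3.1 adds: "Randomization will be done in blocks of four". The SAP's full analysis set (3.2.2) is "all patients who are randomly allocated to a treatment group and received at least 1 dose of effervescent alendronate".

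The two documents rank the endpoint differently. The protocol synopsis makes it primary, to "assess the number of patients that maintain C-terminal telopeptide of type I collagen (CTx-I) levels within the premenopausal reference range at 48 weeks", and Protocol 11.1 repeats this. SAP 4.2 lists as secondary "the number of patients from both groups maintaining CTX-I and PINP levels within reference range values at week 12, 24 and 48". Protocol 11.1 names no test for the count. Protocol 11.3 says that no formal sample size calculation was done and that the number of patients is capped by those who finish the parent study and are willing to join. Neither document gives an expected in-range rate, a target difference, a power, or a reason for choosing Fisher's test.

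**The concern.** Fisher's test conditions on the total number of patients out of range. The design fixes only the arm sizes, not that total. With small arms the conditional p-value takes few values, so a nominal 5% test can operate well below 5%. Recruitment cannot be extended beyond the parent study, so the choice of test is one of the few ways left to gain power on this count. At stake are borderline results that Fisher's test would call non-significant and that a test of exact 5% size would not.

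**Working it through.** **Inputs.** Two-sided rejection if p < 0.05 (SAP 5.3); 20 versus 20 (SAP 2.3). The in-range rates are assumptions, because the documents give none. The CTX-I limits in the footnote to Protocol section 2 are upper limits only, so for CTX-I in range and exceeding are complements and give the same 2x2 table. The plan states no size or power, so there is no figure to reproduce.

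**Formulas.** Let b(i; n, p) be the binomial probability and F(i, j) Fisher's two-sided p-value for i of n1 versus j of n2 in range.
- Size at common rate p: Σ b(i; n1, p) b(j; n2, p) over tables that reject, maximised over a fine grid of p.
- Power: Σ b(i; n1, p1) b(j; n2, p2) over tables that reject.
- Fisher rejects if F < 0.05. Boschloo rejects if F ≤ c, where c is the largest value that keeps the maximum size at or below 5%.

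Fisher's own maximum size is below 5%, so the Boschloo region always contains the Fisher region. This is why Boschloo's test cannot be less powerful.

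**Size at 20/20 (all 21 × 21 tables).** Fisher's maximum is 2.53%, at a common exceedance rate of about 34%. It is 2.26% at a rate of 20%, 2.04% at 50%, 1.18% at 10% and 0.19% at 5%. For Boschloo c = 0.0915, with maximum size 4.64%.

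**One table by hand.** Suppose 18/20 versus 12/20 are in range, so 2 versus 8 exceed and 10 exceed in total. With C(40,10) = 847,660,528:
- P(2) = 190 × 125,970 / 847,660,528 = 0.02824
- P(1) = 20 × 167,960 / 847,660,528 = 0.00396
- P(0) = 184,756 / 847,660,528 = 0.00022

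The sum is 0.03242; doubled by symmetry, p = 0.065. Fisher does not reject. Boschloo does, since 0.065 ≤ 0.0915.

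**Power (%), and gain in points from unrounded powers.** In unequal columns the first-listed rate belongs to the smaller arm.

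| In range | Fisher → Boschloo, 20/20 | Gain 20/20 | 19/19 | 18/18 | 18/20 | 19/20 |
|---|---|---|---|---|---|---|
| 0.90 v 0.60 | 49.2 → 60.9 | 11.7 | 11.9 | 12.6 | 5.7 | 0.1 |
| 0.95 v 0.65 | 58.9 → 69.1 | 10.2 | 10.1 | 9.9 | 2.7 | 0.0 |
| 0.95 v 0.60 | 71.6 → 80.6 | 9.0 | 9.5 | 9.8 | 3.1 | 0.0 |
| 0.90 v 0.50 | 74.2 → 82.2 | 7.9 | 8.8 | 11.1 | 4.8 | 0.3 |
| 0.95 v 0.75 | 29.9 → 37.6 | 7.7 | 6.9 | 6.1 | 1.0 | 0.0 |
| 0.80 v 0.50 | 40.9 → 49.2 | 8.3 | 6.9 | 11.3 | 7.3 | 2.0 |
| 0.70 v 0.30 | 59.9 → 70.5 | 10.6 | 4.1 | 3.7 | 3.4 | 3.9 |
| 0.95 v 0.50 | 89.4 → 94.0 | 4.6 | 5.5 | 6.5 | 2.2 | 0.0 |
| 0.98 v 0.73 | 52.2 → 57.7 | 5.5 | 5.0 | 4.5 | 0.4 | 0.0 |
| 1.00 v 0.75 | 58.5 → 58.5 | 0.0 | 0.0 | 0.0 | 0.0 | 0.0 |

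**Wider grid at 20/20.** Among rate pairs at least 10 points apart where Fisher's power is 30% to 80%, 87% gain 7 to 12 points (median 8.9). Over all such pairs, including those with power near 0 or 1, 37% do (median 5.5). The maximum gain is 11.8.

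**Unequal arms.** Fisher's maximum size is 3.6% at 19/20 and 3.5% at 18/20. The largest gain anywhere on the grid is 4.4 points at 19/20 and 7.8 at 18/20.

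**The case against.** The strongest reply is that nothing here is wrong. Fisher's test is a standard choice for small 2x2 tables and holds the error rate below 5%. The plan promises no power for it to miss, and in the SAP the count is secondary: the primary analysis is a linear mixed model of the marker levels (5.2), which this choice does not touch. All of that stands.

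The second reply is that the gain is fragile, and this stands too. It depends on equal arms, and 20/20 is planned but not assured: the total is a ceiling (Protocol 11.3) and patients never dosed leave the full analysis set (SAP 3.2.2). Counting dosed drop-outs as non-responders does protect the balance under the SAP. Under the per-protocol analysis of week-48 completers in Protocol 11.1, any unequal drop-out would break it. The trial also hopes that nearly all patients stay in range, which is where the gain is smallest.

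A reader might infer that Fisher's test always spends half its error rate here and costs some 7 to 12 points of power whatever happens. The documents do not support that: they give no rates, do not guarantee equal arms, and the loss nearly vanishes at 19/20 in the main scenarios. Nor do they support reading Fisher's test as a fault in the plan's main comparison, since protocol and SAP disagree on which comparison is primary. Changing the test does not settle that disagreement.

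**Conclusion.** The point holds as an optional improvement. At 20 per arm Fisher's test has a true size of at most about 2.5%; Boschloo's test uses up to 4.6%, stays under 5% exactly and rejects every table that Fisher's rejects. With equal arms of 18 to 20, assumed rates and neither arm nearly all in range, the gain is roughly 6 to 13 points. Some pairs give less, such as 0.70 versus 0.30 at 19/19 or 18/18, with about 4. In the first four scenarios of the table it is about 3 to 6 points at 18/20 and almost nil at 19/20. With one arm 98% to 100% in range it is about 0 to 6 points at best. The rates are assumptions throughout. This is lost efficiency, not an error.

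**What to change.** In SAP 5.3, name Boschloo's exact test (two-sided, 0.05) for the week-48 CTX-I in-range comparison, add the risk difference between arms with a 95% CI, and show Fisher's p-value alongside. The interval is worth having whichever test is used, because 5.3 names only a test for this comparison.

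The cost is one line of text and a less familiar test, which the Fisher p-value offsets. No extra patients, visits or data are needed.

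The rule must be fixed before any result is seen. SAP section 6 places finalisation before database lock, yet 5.3 describes the test in the past tense, so the team should confirm which case applies. If results are already known, keep Fisher's test as planned and report Boschloo's only as a labelled sensitivity analysis.

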## 2.2 Hypothesis and objectives

It is hypothesized that effervescent alendronate will be able to maintain bone turnover markers within the reference range thereby reducing the likelihood of bone turnover associated changes, after discontinuation of denosumab treatment in a non-osteoporotic population.

The **primary objective** of this study is to assess the effect of effervescent alendronate after denosumab discontinuation on the change in bone turnover markers after 48 weeks in a non-osteoporotic population and to assess if there is a difference between using oral alendronate after 24 or 48 weeks.

The **secondary objective** is to evaluate the effect of effervescent alendronate after denosumab discontinuation on bone mineral density in this non-osteoporotic population and assess difference in oral alendronate therapy for 24 versus 48 weeks.

**Exploratory objectives** are to study the effect of oral alendronate therapy after denosumab discontinuation on erosive destructive progression at the subchondral bone in erosive hand OA patients and to assess the effect of oral alendronate on their hand pain scores.

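### SAP 5.3 calls any secondary test with p<0.05 statistically significant across 8 to 10 comparisons, with no hierarchy, adjustment or nominal label; the chance of at least one such result when the arms do not differ is roughly 8–30%.

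*SAP*

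**What the plan says.** SAP 4.2 names as secondary endpoints "changes in bone mineral density (BMD) at the femoral neck and spine at week 48" and "the number of patients from both groups maintaining CTX-I and PINP levels within reference range values at week 12, 24 and 48". It adds percentage BMD change and the share of patients losing more BMD than the least significant change.

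SAP 5.3 analyses BMD with a linear mixed model on all available time points and states that "P-values and estimated marginal means will be calculated at different time points". For the counts, "A Fisher's exact test was used to assess differences in patient numbers exceeding reference ranges between both treatment groups". No test is named for the percentage changes or the least-significant-change share. The section ends with the rule "All statistical tests were two-tailed and a p-value below 0.05" (two-sided), and SAP 5.2 has the same rule for the primary analysis: "A p-value below 0.05 (p<0.05) will be considered statistically significant".

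The secondary objective in SAP 2.2 includes the aim to "assess difference in oral alendronate therapy for 24 versus 48 weeks" for bone density. Only new erosive joints and hand pain are labelled exploratory (SAP 2.2 and the exploratory part of SAP 4). Neither the SAP nor protocol section 11 gives a testing order, a condition on the primary result, a division of alpha, a key secondary endpoint, or a statement that secondary p-values are descriptive.

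**The concern.** Unadjusted secondary tests are acceptable when they are presented as supportive. This SAP attaches the words statistically significant to each of them and does not limit which site, marker or visit may carry a conclusion. In a study of about 20 per arm with no sample size calculation (protocol 11.3), one isolated p<0.05 is weak evidence. As written, it may be reported as a significant difference between 24 and 48 weeks even when the primary comparison shows nothing.

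Two features make this more than routine. First, several comparisons are made before the arms differ in treatment. Second, the family contains the week-48 CTX-I in-range count, which the protocol (sections 2 and 11.1) names as its primary endpoint, although SAP 4.2 lists it as secondary.

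**Working it through.** The documents give no family-wise figure to reproduce. The only stated figure is the per-test two-sided 0.05.

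**Counting the comparisons**

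- BMD as listed in SAP 4.2: 2 sites × week 48 = 2.
- Counts as listed in SAP 4.2: 2 markers × 3 visits = 6.
- Total listed: 2 + 6 = 8.
- DXA is also done at week 24 (protocol 5.1 and study table). If the SAP 5.3 sentence on p-values at different time points applies to that visit, 2 more are added, giving 10.
- Week 48 only: 2 BMD + 2 counts = 4.

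**Inputs**

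- 20 per arm (protocol 3.1, SAP 2.3).
- Per-test level 0.05, two-sided (SAP 5.3).
- Assumed, because the documents give neither: the share out of range (2–50%, the same in both arms; it would include drop-outs, whom SAP 3.2.3 counts as non-responders) and the correlations.

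**Size of Fisher's exact test at 20 versus 20.** The test is conservative here: 0.0019 at a true share of 5%, 0.0118 at 10%, 0.0226 at 20%, 0.0248 at 30%, 0.0204 at 50%.

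**Independent tests.** The chance of at least one rejection is 1 − 0.95^b × (1 − s)^f, with b BMD tests, f Fisher tests and s the Fisher size.

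- Share 5%, 8 tests: 1 − 0.95² × 0.9981⁶ = 0.108.
- Share 10%, 8 tests: 1 − 0.95² × 0.9882⁶ = 0.160.
- Share 30%, 8 tests: 1 − 0.95² × 0.9752⁶ = 0.224.
- Share 30%, 10 tests: 1 − 0.95⁴ × 0.9752⁶ = 0.299.
- Share 30%, week 48 only: 1 − 0.95² × 0.9752² = 0.142.

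**Correlated tests.** The table comes from a simulation of 20,000 trials per scenario with no arm difference. Two-sample t-tests stood in for the mixed-model BMD contrasts. Correlations ran from 0 up to 0.7 between markers and between marker visits, 0.6 between BMD sites and 0.8 between BMD visits.

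| Share out of range | Four week-48 tests | 8 listed tests | 10 tests |
|---|---|---|---|
| 2% | 0.086–0.097 | 0.087–0.097 | 0.135–0.184 |
| 5% | 0.087–0.101 | 0.092–0.108 | 0.141–0.193 |
| 10% | 0.109–0.118 | 0.147–0.158 | 0.191–0.236 |
| 20% | 0.125–0.141 | 0.190–0.208 | 0.232–0.294 |
| 30% | 0.127–0.142 | 0.198–0.224 | 0.238–0.298 |
| 50% | 0.125–0.136 | 0.179–0.203 | 0.226–0.289 |

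A second simulation, with one common correlation across all endpoints, gave 0.078–0.081 for the two week-48 BMD tests alone at correlation 0.8. That sets the lower end near 8%, because the counts add almost nothing if few patients leave the range.

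**Comparisons that cannot reflect duration.** Both arms take the same weekly alendronate until week 24 (protocol 3.1 and 4.1). The counts at weeks 12 and 24 (2 markers × 2 visits = 4) and the week-24 BMD contrasts (2) make 6 of the 10, or 4 of the 8 listed. If independent, the six give 1 − 0.95² × 0.9981⁴ = 0.104 at a share of 5% and 1 − 0.95² × 0.9752⁴ = 0.184 at 30%.

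**The case against.** The strongest reply is that the SAP already ranks its endpoints as primary, secondary and exploratory, that this is a single-site, open-label study of 40 patients, and that nominal secondary p-values are common in that setting. This largely stands and keeps the point modest. It does not cover the missing label: nothing in the SAP says the p-values are nominal.

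A reader might infer three stronger things, none of which the documents support.

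- **That the SAP breaks a promised 5% error rate.** It does not. Its 0.05 is a per-test threshold, and neither document states a family-wise rate. Nor do the documents fix one inflation figure, since correlation and out-of-range share are not given.
- **That any site, marker or visit could credibly answer the duration question.** Results at weeks 12 and 24 cannot, because the regimens have not yet diverged. The SAP 2.2 secondary objective concerns BMD only, and at week 48 that is two tests.
- **That a fixed testing sequence conditional on the primary result is the remedy.** SAP 4.1 names two primary markers and no single contrast, so the condition would be undefined. A blanket ban on claiming significance would also cover the week-48 CTX-I count, the protocol's own primary endpoint.

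It is also fair to say that SAP 4.2 lists BMD at week 48 only, so 8 is the firmer count and 10 depends on how SAP 5.3 is read. The similar gap at the primary level (two markers, p-values at several time points) matters more, but it is a separate point.

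**Conclusion.** The point holds in a limited form and is a cheap improvement. SAP 5.3 allows any of 8 secondary comparisons (10 on the wider reading) to be called statistically significant at a per-test 0.05, with no order, adjustment or nominal label. With no arm difference and 20 per arm, the chance of at least one such result is roughly 8–30%. For the four week-48 tests alone it is about 8–15%, the upper end rounded up from 14.2%. Every scenario examined is above 5%.

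These figures rest on assumed out-of-range shares, assumed correlations and t-tests in place of the mixed model. They already allow for the conservatism of Fisher's test. The conclusion about weeks 12 and 24 needs none of these assumptions: it follows from the design.

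**What to change.** First reconcile the status of the week-48 CTX-I in-range count, which is primary in protocol sections 2 and 11.1 and secondary in SAP 4.2. The text below should apply to it only if it stays secondary.

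Then replace the last sentence of SAP 5.3 with:

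> Secondary endpoints are reported as between-arm estimates with 95% confidence intervals and nominal two-sided p-values, unadjusted for multiplicity, and are interpreted as supportive. Between-arm comparisons at weeks 12 and 24 are descriptive and will not be used to claim a difference between 24 and 48 weeks.

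No formal testing sequence is needed. The cost is two sentences in the SAP and matching wording in the report, with no new patients or data. The downside is that an isolated secondary p<0.05 can no longer be presented as a confirmed effect of treatment duration.
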